4.2.1. CHOP-INTEND Score

There are 16 items in CHOP-INTEND assessment (Section **Error! Reference source not found.**). A rating of Brazelton behavioral states (Section **Error! Reference source not found.**) was recorded for each item. As suggested by manual [9], the optimal state for testing is state 4 (“alert, with bright look”) and 5 (“eyes open”). If a subject cannot be tested for an item due to an adverse behavioral state, it should be scored as “CNT” (cannot test) and NOT a zero. In item 1 to 11, 13 and 16, both left and right sides need to be evaluated, and the maximum score should be selected for the best score of the item. If both sides are scored “CNT”, the item should be scored as “CNT”. If only one side scored “CNT”, the other side score should be used for the best score

of the item. If any of these 16 items scored “Cannot test” or “CNT”, the total score should be set missing.

4.3. Safety Endpoints

Safety endpoint include physical examinations, pulmonary examinations, vital signs, capillary blood gas assessments, weight and length measurements, 12-lead ECGs, echocardiograms, 24-hour Holter monitors, swallowing tests, laboratory assessments, adverse event monitoring, and photographs of the infusion site. In general, safety assessments will be performed at the times scheduled in Table 1. All post-treatment visits are relative to the date on which gene replacement therapy is administered until the patient is 14 months of age, after which all visits will be relative to the patient’s date of birth.

The primary safety endpoint is the development of unacceptable toxicity, defined as the occurrence of any one Grade III or higher, unanticipated, treatment-related toxicity that presents with clinical symptoms and requires medical treatment

4.4. Pharmacokinetic Endpoints

Not applicable for this SAP.

4.5. Pharmacodynamics Endpoints

Not applicable for this SAP.

4.6. Additional Safety Endpoints

Additional safety analyses include:

4.6.1. Adverse Events

Other than Grade III or higher adverse events used to define unacceptable toxicity in the primary endpoint, all adverse events will be assessed for their seriousness, relatedness to study treatment, relationship to study discontinuation, and severity according to [CTCAE](#) version 4.03 criteria.

4.6.2. Vital Signs

Length, weight, blood pressure, respiratory rate, pulse, body temperature, and pulse oximetry will be collected at every visit. For detailed schedule of events table, see [Table 1](#).

4.6.3. Physical Examination

Physical examination will include review of the following systems: head, eyes, ears, nose, throat (HEENT), lungs/thorax, cardiovascular, abdomen, musculoskeletal, neurologic, dermatologic, lymphatic, and genitourinary.

4.6.4. Laboratory Evaluations

Blood will be collected throughout the study for standard blood chemistry and hematology tests as well as cardiac enzymes. Urine will be collected throughout the study for standard urinalysis exams.

4.6.5. Use of Non-Oral Feeding Support

A swallowing test will be performed at baseline and every 6 months to determine if the patient has signs of aspiration. If the test is positive for aspiration, the patient will be recommended to use an alternative method to oral feeding. Once implanted, a non-oral method of feeding support may later be removed. For each placement or removal event, the type of support (type of tube), date of placement, and date of removal will be noted. Actual use of non-oral feeding support will be quantified through the recording of volume, frequency of use, duration, and calories.

4.6.6. Pulse Oximetry

Pulse oximetry will be measured throughout the study through a small infrared light attached to the end of the patient's finger.

4.6.7. Cardiovascular Safety Evaluations

A 12-lead electrocardiograms will be conducted on the schedule of assessment (Table 1). The ECG tracings or ECG machine data will be collected for centralized review and interpretation by a cardiologist.

A Holter monitor and serial ECG data collected at the scheduled time points. Twenty-four hour Holter monitoring will also be performed starting from Month 3 and every 3 months thereafter until 12 months post-dose and again at 18 months of age.

4.6.8. Immunology

Immunoreactivity to AAV9 and SMN will be measured in antibody titer levels (in 2-fold serial dilutions) as determined by enzyme-linked immunosorbent assays (ELISAs). T-cell response to AAV9 and SMN will be measured in number of spot forming cells per million peripheral blood mononuclear cells (PBMCs) as determined by Enzyme-Linked ImmunoSpot (ELISpot) assays.

4.6.9. Concomitant Medications

Prior and concomitant medications will be captured in the eCRF from two weeks prior to study dosing through the last study visit and coded using the WHO Drug dictionary, most recent version available.

4.6.10. Non-invasive Ventilatory Support

Patients will be assessed by a pulmonologist at the time points specified in the schedule of assessments and may be fitted with a non-invasive positive pressure ventilator (e.g., Bilevel Positive Airway Pressure (BiPAP)) at the discretion of the pulmonologist and/or investigator. Non-invasive ventilatory support equipment may be provided by AveXis, Inc. through a third-party vendor (as necessary).

Each patient will be assessed by investigator whether permanent ventilation criteria has been met. If the patient meets the permanent ventilation criteria, the date of permanent ventilation met will be reported through [REDACTED]. Also, if [REDACTED] machine is used with SD card, the daily real hours of usage data will be sent to AveXis. Health-economics Endpoints

The analysis of healthcare resource utilization data may be performed for this study.

4.7. Other Endpoints

Additional analyses of the primary, secondary, and other additional endpoints utilizing a natural history cohort as a comparison may be incorporated, as appropriate.

5. ANALYSIS POPULATION

Safety will be assessed based on all patients who underwent gene therapy at day 1. The primary population for the primary and secondary efficacy analyses will be the ITT population. If enrolled, patients with 1 copy of *SMN2*, pre-symptomatic patients and patients with the *SMN2* gene modifier mutation (c.859G>C) and other permutations outside of those specified in the ITT population will be evaluated separately as part of additional subgroup analyses.

5.1. Safety Population

All patients who underwent gene therapy infusion will be included. All safety analyses will be based on the safety population, unless specified otherwise.

5.2. Intent-to-Treat (ITT) Population

The ITT population will consist of symptomatic patients with bi-allelic deletion of *SMN1* (exon 7/8 common homozygous deletions) and 2 copies of *SMN2* without the known gene modifier mutation (c.859G>C) who receive an IV infusion of AVXS-101 at less than 180 days of age.

5.3. Ability to Thrive ITT Population

The ability to thrive ITT population will consist of symptomatic patients with biallelic deletion mutations of *SMN1*, 2 copies of *SMN2* without the genetic modifier (c.859G>C), intact swallowing and receiving no enteral (mechanical) nutrition at baseline, who receive an IV infusion of AVXS-101 and have at least one post-baseline efficacy evaluation.

5.4. Efficacy Completers Population

The efficacy completers analysis population will consist of:

- All treated patients who reach 14 months of age for the survival endpoint or 18 months of age for the endpoint of achievement of sitting without support, OR
- All treated patients who meet discontinuation criteria, discontinue the study due to an AE, or experience death

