14.1.1.3. Efficacy Completers Population

The efficacy completers analysis population will consist of:

- All treated patients who reach 14 months of age, OR
- All treated patients who meet discontinuation criteria, discontinue the trial due to an AE or death

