3.6. Patient Selection

The current version of the protocol (v7.0) allows for enrollment up to 30 patients, who are 6 months of age or younger at time of gene replacement therapy infusion (Day 1) diagnosed with SMA Type 1 who meet enrollment criteria, which may be either symptomatic or pre-symptomatic and are genetically defined by no functional survival motor neuron 1 gene (*SMN1*) as well as 1 or 2 copies of survival motor neuron 2 gene (*SMN2*). Enrolling up to thirty (30) patients under the broader enrollment criteria is projected to enable enrollment of at least twenty-five (25) patients that meet the Intent-to-Treat Population (ITT) criteria. The ITT population is identified as symptomatic patients with bi-allelic *SMN1* deletions and 2 copies of *SMN2* without the *SMN2* gene modifier mutation (c.859G>C) who meet all other study enrollment criteria. Patients with 1 copy of *SMN2*, pre-symptomatic patients and patients with the *SMN2* gene modifier mutation (c.859G>C) and other permutations outside of those specified in the ITT population will be evaluated separately as part of additional subgroup analyses. Details of all analyses will be contained within this Statistical Analysis Plan.

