6.7. Subgroups

Two subgroups based on age at dosing (study day 1) will be assessed in the selected analysis (developmental milestones and statistical modeling parts):

- Patients with age at dosing (study day 1) \leq 4 months (120 days)

- Patients with age at dosing (study day 1) > 4 months (120 days).

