7. DEMOGRAPHIC, OTHER BASELINE CHARACTERISTICS AND MEDICATION

7.1. Patient Disposition and Withdrawals

Patient disposition will be presented for all patients, which will include the following:

- The number of patients screened
- The number (%) of screened patients who screen failed and the reasons for screen failure (inclusion/exclusion criteria, withdrew consent, and/or other) will be summarized. A listing of reason for screen failure will be provided for all patients who screen failed.
- The number (%) of patients in the safety population
- The number (%) of patients in the Efficacy Completer Population
- The number (%) of patients reach the 14 months of age for survival endpoint
- The number (%) of patients who completed the study, defined as all patients with a final scheduled visit conducted either remotely or at the study site
- The number (%) of patients who discontinued from the study and the associated reasons

For patients who discontinued due to AE, a separate summary table will be produced in order to detail the type of AE that resulted in the discontinuation (whether serious fatal, non-serious fatal, or non-fatal).

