8.3. Exploratory Efficacy Endpoint(s) and Analyses

The exploratory efficacy analyses will be based on Efficacy Completers Population. Due to COVID-19 impact, any efficacy data collected outside of the SAP-defined visit window of Month 18 of age visit (older than 570 days of age) will be grouped into “Month 19 of age or older” and included for summary tables unless specified. The hypothesis testing will be based on the data collected up to 18 months of age. Those data will also be included in the corresponding listing.

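### SAP 8.3 runs 18 exploratory tests on all treated completers, pooling any non-ITT infants that SAP 3.6 and 5 say are evaluated separately, and specifies neither an ITT rate nor a non-ITT summary for those endpoints

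*SAP*

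**What the plan says.** **Population for the exploratory tests.** SAP 8.3 opens with "The exploratory efficacy analyses will be based on Efficacy Completers Population". Protocol 14.1.1.3 starts the definition of that population with "All treated patients who reach 14 months of age, OR". SAP 5.4 keeps the all-treated basis, adds 18 months of age for the sitting endpoint, and gives as its second limb "All treated patients who meet discontinuation criteria, discontinue the study due to an AE, or experience death". Neither document restricts the set by symptoms, SMN2 copy number or modifier status.

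**Promise of separate evaluation.** SAP 3.6 lists one-copy, pre-symptomatic and modifier infants and then "other permutations outside of those specified in the ITT population will be evaluated separately as part of additional subgroup analyses". It goes on: "Details of all analyses will be contained within this Statistical Analysis Plan". SAP 5 repeats that such infants, if enrolled, "will be evaluated separately as part of additional subgroup analyses".

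**Subgroups actually defined.** SAP 6.7 says "Two subgroups based on age at dosing (study day 1) will be assessed in the selected analysis", with a cut at 120 days. The milestone paragraphs of SAP 8.3, where they name a subgroup, name only age at treatment.

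**Where ITT is used.** SAP 8.1.1 reports 10-second sitting on ITT and repeats the analysis on completers. Survival is analysed on ITT. Ability to thrive has its own ITT-type set (Protocol 14.1.1.2.2, SAP 5.3). The disposition list in SAP 7.1 includes "The number (%) of patients in the Efficacy Completer Population" but has no ITT line.

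**Whether such infants are expected.** The statistical methods in the protocol synopsis foresee a small number of patients beyond the ITT definition. Protocol inclusion criterion 1 admits one-copy and modifier infants, and SAP 3.6 admits pre-symptomatic infants.

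**The concern.** Following SAP 8.3 as written puts every treated completer into one denominator and tests the pooled proportion against 0.1%. Protocol 14.2 and SAP 3.7 argue that null from the natural history of the ITT-type population. Protocol 5.2 says Type 1 patients in general never sit independently, so the argument extends in part to others. It fits least well for modifier infants and some pre-symptomatic infants.

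The plan also treats nearly the same patients in two ways. SAP 5.5 calls analyses of all infused patients descriptive. SAP 5.4 gathers almost all of those patients into the completers set, and 8.3 tests hypotheses on it.

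At stake is how the exploratory milestone and CHOP-INTEND rates are read. If non-ITT infants are enrolled, those rates describe a mixture, and no summary named in the SAP gives the ITT component or the non-ITT component.

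**Working it through.** **Inputs from the documents**
- Planned enrolment 30, at least 25 of them ITT (Protocol 14.2, SAP 3.7).
- Null 0.1%, one-sided exact binomial test (SAP 8.3.1 onward). One-sided level 0.025 (SAP 6.1).
- Assumed true response rate 20% to 50%, power above 95% at n=25 (SAP 3.7).
- Phase 1 Cohort 2: 16.7% for each of the standing and walking milestones (Protocol 5.4).

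**Assumption.** 25 ITT and 5 non-ITT infants are treated and all are completers. The documents do not give the actual mix.

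**Number of tests.** 8.3.1 to 8.3.14 give 14, 8.3.17.1 to 8.3.17.3 give 3, and 8.3.17.4 gives 1: 14 + 3 + 1 = 18. Ability to thrive is left out because it has its own set.

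**Plan's own figure.** At n=25, P(X≥1 | 0.1%) = 1 − 0.999^25 = 0.0247, below 0.025, so one responder rejects. Power at 20% is 1 − 0.8^25 = 0.9962, and at 50% it is above 0.9999. The stated power above 95% is reproduced.

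**Same test on the pooled set, n=30**
- P(X≥1 | 0.1%) = 1 − 0.999^30 = 0.0296, above 0.025, so one responder no longer rejects.
- P(X≥2 | 0.1%) = 1 − 0.999^30 − 30 × 0.001 × 0.999^29 = 0.0004, so two are needed.
- The change comes at n=26, where 1 − 0.999^26 = 0.0257.
- Power at 20% is 1 − 0.8^30 − 30 × 0.2 × 0.8^29 = 0.9895. At 50% it is above 0.9999.

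**Estimates.** With x ITT achievers of 25 and k non-ITT achievers of 5, the pooled rate is (x + k)/30. The extremes are k=0 and k=5.

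| ITT result | Pooled, k=0 | Pooled, k=5 |
|---|---|---|
| 5/25 = 20% | 5/30 = 16.7% | 10/30 = 33.3% |
| 4/25 = 16% | 4/30 = 13.3% | 9/30 = 30.0% |
| 2/25 = 8% | 2/30 = 6.7% | 7/30 = 23.3% |

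With only 2 non-ITT infants, 4/25 could read 4/27 = 14.8% to 6/27 = 22.2%. For scale, the exact two-sided 97.5% interval for 4/25 is 3.7% to 38.9%.

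**Decisions for rare milestones**
- One ITT achiever and no others: 1/25 rejects (p=0.0247), 1/30 does not (p=0.0296).
- No ITT achiever and two non-ITT achievers: 2/30 gives p=0.0004, significant with 0/25 in ITT.
- ITT infants at the 0.1% null and non-ITT infants at an assumed rate q: the pooled test rejects with probability 0.090 at q=10%, 0.27 at 20% and 0.82 at 50% (25 + 5 infants).
- True rate 8% in everyone: rejection probability is 1 − 0.92^25 = 0.876 at n=25, and 1 − 0.92^30 − 30 × 0.08 × 0.92^29 = 0.704 at n=30.

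**The case against.** The strongest defence is that 8.3 breaks no protocol rule. Protocol 14.1.1.1.3 words the exploratory endpoints for patients, without the genotype and symptom limits of the primary and secondary endpoints, and Protocol 14.1.1.2.1 ties ITT to the primary and secondary analyses only. Separate evaluation could also be meant as an addition to a pooled summary. Both points stand. They place the conflict inside the SAP, which promises a separate evaluation, says it holds all details, and then specifies none.

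Two rules already limit inflation. SAP 4.2 does not count milestones seen at baseline, and SAP 8.3.17 drops infants at or above a CHOP-INTEND threshold at baseline. Better-functioning infants can therefore raise the rates less than a simple pooling argument suggests, and CHOP-INTEND denominators need not be 25 or 30. Nor is the direction fixed: the survival figures in Protocol 5.2 suggest that one-copy infants would more likely lower the rates.

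Three stronger readings are tempting, and the documents do not support them:
- *The exploratory rates cannot be set beside the primary sitting rate.* SAP 8.1.1 repeats the 10-second analysis on completers, so a matched rate exists if that set means all treated. If it means ITT-type patients, 8.3 pools nobody. The two sitting items also differ by definition, since the Bayley item allows use of the arms.
- *No output could separate the groups.* Listings are planned (SAP 4.1.1, 6.4.1, 8.3), and display details are left to separate table documentation. What is missing from the SAP text is a summary.
- *The confirmatory result is contaminated.* The primary and secondary tests are on ITT, and the 8.3 tests lie outside the hierarchy in SAP 8.4.

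**Conclusion.** The point holds as an inconsistency within the SAP that should be corrected. Its reach is the 18 exploratory tests and their estimates, and only if non-ITT infants are enrolled. The confirmatory tests and their power are untouched.

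The size rests on the assumed 25 + 5 split, and the rate ranges are extremes (none or all of the five achieving). On that basis a 16% ITT rate could be displayed as 13.3% to 30.0%, which is still inside the exact interval for 4/25. At the planned 20% to 50% response the decision is practically the same on either set. For rare milestones it can change in both directions, including a significant result with no ITT achiever.

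**What to change.** - **SAP 8.3:** run the tests against 0.1% on completers who also meet the ITT criteria, or on ITT. Keep the all-treated completers summary as descriptive.
- **SAP 6.7 or 8.3:** add a descriptive summary of non-ITT infants, so that the statements in 3.6 and 5 are carried out.
- **SAP 8.1.1:** state whether the completers repeat of the primary analysis is limited to ITT-type patients. If it is, note that it will be close to the ITT result.
- **SAP 13:** record the change, next to the existing entry on the completers definition.
- **SAP 7.1:** an ITT count in the disposition list is optional, since 8.1.1 already reports number and percent for ITT.

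The cost is wording and one extra descriptive summary on data already collected. Exploratory test denominators fall by up to about 5 under the assumed split.

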5.5. All Enrolled Population

The all enrolled population will consist of all patients who receive an IV infusion of AVXS-101. Analyses of endpoints in this population are considered descriptive. For AVXS-101-CL-302, all enrolled population is the same as safety population.

5.6. PNCR Control Population

The PNCR Natural History dataset is drawn from a large natural history study ([Finkel, 2014](#)) performed on a large cohort of 337 patients with any form of spinal muscular atrophy followed at 3 large, internationally recognized tertiary medical centers with significant expertise in the management of SMA (Harvard University/Boston Children's Hospital, Columbia University and the University of Pennsylvania/Children's Hospital of Philadelphia). Previously identified patients followed in PNCR site clinics and newly diagnosed patients were enrolled. All eligible patients were offered participation in the PNCR study. Study visits were scheduled at baseline and at 2, 4, 6, 9, and 12 months and every 6 months thereafter. The SMA standard of care

guidelines ([Wang, 2007](#)) were used as a basis for providing uniform care among the study sites. For purposes of this study, sitting (for SMA Type 2) was defined as being able to sit independently for >10 seconds; children who were unable at any point to achieve this milestone were classified as SMA Type 1.

A natural history control population is drawn from the PNCr Natural History Dataset ([Finkel, 2014](#)) consisting of all patients with age of onset ≤ 6 months, bi-allelic deletion of *SMN1* (exon 7/8 common homozygous deletion) and 2 copies of *SMN2* for whom enrollment data (retrospective and prospective) is available to determine survival based on the defined criteria. The *SMN2* modifier mutation (c.859G>C) described by Prior and colleagues (Prior, Thomas W., et. al. "A positive modifier of spinal muscular atrophy in the *SMN2* gene." *The American Journal of Human Genetics* 85.3 (2009): 408-413.) was not assessed in the PNCr study cohort. Based on these criteria, 23 patients from the PNCr dataset are included in the control population. Among them, 16 patients reached the combined endpoint of death or the need for a minimum of 16 hours/day of noninvasive ventilation support for a minimum of 14 continuous days by 14 month of age and one patient discontinued the study at age of month 4. The survival rate at 14 months of age is approximately 25% (6/23), of which the control cohort will be used as comparator with ITT population for survival analysis.

